#### 4.3.5. Imputation of Incomplete Dates

An incomplete date is any date for which either the day, month or year is unknown, but at least one field is known. An incomplete date occurs when the exact date an event occurred or ended cannot be obtained from a subject. For many of the analyses, a complete date is necessary in order to determine if the event should be included in the analysis (i.e., if the event is treatment-emergent) or to establish the duration of an event. In such cases, incomplete dates will be imputed.

For purposes of imputation, all events with an incomplete end date are assumed to have ended on or before the day the form was completed. In an effort to minimize bias, the project statistician will impute incomplete start dates in a systematic, but reasonable manner. For diary data, missing dates

will be imputed based on the nominal visit day relative to Day 1. For other data, if the month/year is the same as the Day 1 month/year then the date will be set to the date of Day 1. In other cases, missing days will be imputed as the day component of Day 1; missing months/years will be imputed as the month/year of Day 1. A list of incomplete and imputed dates will be prepared by the project statistician or statistical programmer(s) and will be submitted for review by the clinical project manager and sponsor.

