11.1.1.2. Serious Adverse Event

An SAE is an adverse event that results in any of the following outcomes:

- Death
- Is life-threatening (subject is at immediate risk of death at the time of the event; it does not refer to an event that hypothetically might have caused death if it were more severe)
- Requires in-subject hospitalization (formal admission to a hospital for medical reasons) or prolongation of existing hospitalization
- Results in persistent or significant disability/incapacity (i.e., there is a substantial disruption of a person's ability to carry out normal life functions)
- Is a congenital anomaly/birth defect

Important medical events that may not result in death, are not life-threatening, or do not require hospitalization may be considered an SAE when, based upon appropriate medical judgment, they may jeopardize the subject or may require medical or surgical intervention to prevent one of the outcomes listed in this definition. Examples of such events include allergic bronchospasm requiring intensive treatment in an emergency room or at home, blood dyscrasias or convulsions that do not result in subject hospitalization, or the development of drug dependency or drug abuse.

Hospitalization, as per the institution's standard of care (SOC) to treat pediatric influenza is not considered an SAE and should not be reported as such. Any adverse event the causes a prolongation of an existing hospitalization must be reported as per Section 11.1.5.

11.1.2. Method, Frequency, and Time Period for Detecting Adverse Events and Reporting Serious Adverse Events

Reports of AEs are to be collected from the time the subject consents to participate through the follow-up period ending on Day 14. The Investigator or designee must completely and promptly record each AE. The Investigator should attempt, if possible, to establish a diagnosis based on the presenting signs and symptoms. In such cases, the diagnosis should be documented as the AE and not the individual sign/symptom. If a clear diagnosis cannot be established, each sign and symptom must be recorded individually. If a final diagnosis is established during evaluation or treatment, the source documents will be updated accordingly.

The Investigator should attempt to follow all unresolved AEs and/or SAEs observed during the study until they are resolved, or are judged medically stable, or are otherwise medically explained.

11.1.3. **Definition of Severity**

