#### 4.2. RANDOMIZATION AND MASKING

Approximately 140 subjects will be enrolled. Up to 10 subjects from birth to < 28 days will be enrolled to receive a single dose of IV peramivir. Up to 20 subjects from 28 days to < 2 years will either be randomized to 1 of 2 treatment arms at a ratio of 4:1 or will receive a single dose of IV peramivir. Up to 110 subjects from 28-days to < 18 years of age will be randomized to 1 of 2 treatment arms at a ratio of 4:1:

- Treatment Group 1: A single dose of IV peramivir
- Treatment Group 2: Oral oseltamivir given BID for 5 days

This is an open label study and as such, blinding is not applicable.

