#### Treatment-emergent Adverse Event

Any event reported on the CRF that occurs on or after the initiation of study drug and not more than 14 days after the last dose of study medication is considered treatment-emergent. Additionally, it is assumed that an Adverse Event which was reported to have started on Day 1 without an associated onset time may have occurred after the initiation of study drug. Hence, Adverse Events occurring on Day 1 with no associated onset time are assumed to be treatment-emergent.

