#### 6.3. SAFETY

#### **6.3.1.** Adverse Events

Adverse events will be mapped to a Medical Dictionary for Regulatory Activities (MedDRA) version 18.0 preferred term and system organ classification. If a subject experiences multiple events that map to a single preferred term, the greatest severity grade and strongest investigator assessment of relation to study medication will be assigned to the preferred term for the appropriate summaries. Should an event have a missing severity or relationship, it will be classified as having the highest severity and/or strongest relationship to study medication. Summaries of treatment-emergent AEs will include any AEs reported beginning with the initiation of study drug on Day 1. The occurrence of treatment-emergent adverse events (TEAEs) will be summarized by treatment group using preferred terms, system organ classifications, and severity. Separate summaries of treatment-emergent serious adverse events, treatment-emergent adverse events related to study drug, and events leading to the discontinuation of study will be generated. All adverse events reported will be listed for individual subjects showing both verbatim and preferred terms. All adverse events that occurred prior to the initiation of study treatment or more than 14 days post-study drug discontinuation will be excluded from the tables but will be included in the listings.

Missing onset dates will be imputed as previously outlined in Section 4.3.5 as required to determine treatment-emergent events.

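### An adverse event start date with a missing day and a month later than the Day 1 month is imputed 28 to 31 days after Day 1, always outside the treatment-emergent window

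*SAP*

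**What the plan says.** SAP 4.3.5 covers dates with at least one known component. Diary dates follow the nominal visit day. For all other data, including adverse events, the rule has two branches:

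- Same month and year as Day 1: "if the month/year is the same as the Day 1 month/year then the date will be set to the date of Day 1".
- Anything else: "In other cases, missing days will be imputed as the day component of Day 1". A missing month or year is taken from Day 1.

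SAP 6.3.1 makes this imputation decide treatment-emergent status: "Missing onset dates will be imputed as previously outlined in Section 4.3.5 as required to determine treatment-emergent events". SAP 4.3.8 defines the window: an event on or after the start of study drug and "not more than 14 days after the last dose of study medication is considered treatment-emergent". SAP 6.3.1 gives the consequence of falling outside it: events "more than 14 days post-study drug discontinuation will be excluded from the tables but will be included in the listings".

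Protocol 11.1.2 has adverse events collected from consent "through the follow-up period ending on Day 14". SAP 2.1 names the incidence of treatment-emergent adverse events as a primary safety endpoint, together with treatment-emergent laboratory changes. SAP 4.3.5 also says that the imputed dates will be listed and reviewed by the clinical project manager and the sponsor.

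**The concern.** Follow-up lasts about two weeks, so an event recorded in the month after dosing must have begun early in that month. Placing it on Day 1's day number pushes it about a month past dosing, to a time when the study was no longer collecting events. The filter then removes it from the tables.

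This runs against the rest of the SAP, which settles missing adverse event data conservatively. A Day 1 event with no onset time counts as treatment-emergent (SAP 4.3.8). A missing severity or relationship takes the highest or strongest value (SAP 6.3.1). A partial date in the Day 1 month becomes Day 1. Only the later-month branch drops the event, although the section states that it aims to limit bias. The separate tables of serious and of drug-related treatment-emergent events are also at risk, because they use the same definition.

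**Working it through.** The plan gives no figure to reproduce. The check applies the rule to the calendar.

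**Inputs**

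- Last dose: Day 1 for peramivir (SAP 4.2, "Treatment Group 1: A single dose of IV peramivir"). For oseltamivir, twice daily for 5 days, it is Day 5, or Day 6 if the first dose is given late in the day (assumption).
- Window: 14 days after the last dose (SAP 4.3.8).
- Collection: to Day 14, which is 13 days after Day 1 (Protocol 11.1.2).
- Enrolment: December 2014 to September 2020 (estimated, Protocol synopsis), which is 70 months and 2,131 possible Day 1 dates.

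**Window close, in days after Day 1**

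- Peramivir: 0 + 14 = 14 (Study Day 15).
- Oseltamivir: 4 + 14 = 18 (Study Day 19), or 5 + 14 = 19 with a Day 6 last dose.

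**Imputed gap**

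The same day number one month later lies exactly one Day 1 month away, so the gap is 28, 29, 30 or 31 days. The smallest, 28, exceeds 14, 18 and 19. No Day 1 date makes the rule work.

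**Worked case: Day 1 on 25 January 2016, onset recorded as February 2016 with no day**

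- Imputed onset: 25 February, 31 days after Day 1, Study Day 31 + 1 = 32.
- Day 14: 25 January + 13 days = 7 February, so a true onset by Day 14 lies between 1 and 7 February.
- Window close: 8 February for peramivir; 12 February for oseltamivir with a Day 5 last dose.
- Every possible true onset by Day 14 is in the window in both arms; the imputed one is outside it in both.

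**All Day 1 dates in the enrolment period**

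Day 14 falls in the next month when Day 1 is one of the last 13 days of its month: 70 × 13 = 910 of 2,131 dates (42.7%).

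| Length of Day 1 month | Months | Day 1 dates | Imputed date does not exist | Imputed date exists |
|---|---|---|---|---|
| 28 days | 4 | 52 | 0 | 52 |
| 29 days | 2 | 26 | 0 | 26 |
| 30 days | 23 | 299 | 0 | 299 |
| 31 days | 41 | 533 | 39 | 494 |
| Total | 70 | 910 | 39 | 871 |

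Of the 871 dates that exist, none is within 14, 18 or 19 days of Day 1. The 39 others have no imputed onset at all; 31 January, for example, gives 31 February.

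**Share of onset days exposed**

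If onsets are uniform over Days 1 to 14 and Day 1 is uniform over the calendar (both assumptions), the mean offset is 6.5 days and the mean month is 2,131 / 70 = 30.4 days. Then 6.5 / 30.4 = 21.4% of onset days fall in the next month. Only events there that also lack a day are affected, and the documents give no rate of missing days.

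**Size of one lost event**

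Protocol 13.4 plans about 117 of 140 subjects on peramivir, leaving about 23 on oseltamivir. If the lost event is a subject's only one, incidence falls by 1/117 = 0.9 percentage points on peramivir or 1/23 = 4.3 points on oseltamivir. In the birth to under 28 days cohort of up to 10 subjects, it falls by 10 points if that cohort is full.

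**The case against.** The strongest reply is that this will rarely matter. It needs follow-up that crosses a month end, an onset after the crossing and a missing day. Adverse events are recorded at contacts on Days 1, 3, 7 and 14 (Protocol 11.1), and the investigator must record each one fully and promptly (Protocol 11.1.2). An onset near Study Day 30 should stand out when the imputed dates are reviewed. Excluded events remain in the listings, no hypothesis is tested, and the error applies to both arms. All of this stands and limits the likely size. It does not repair the rule: the review has no stated basis for changing a date, and incidence is read from the tables.

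A reader might infer more than the documents support:

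- **That the whole rule is wrong.** It is not. A month before Day 1 yields a pre-treatment date, as it should, and a missing month or year filled from Day 1 is conservative.
- **That about a fifth of adverse events are lost.** The 21.4% is a share of onset days under uniform assumptions, before requiring a missing day.
- **That the imputed onset must contradict the end-date assumption.** The section says that "all events with an incomplete end date are assumed to have ended on or before the day the form was completed", but no completion date is given. Unresolved events are followed beyond Day 14, so the form may be completed later.
- **That the window itself needs changing because it closes at different study days in the two arms.** Anchoring on the last dose gives each arm the same time after exposure, which is a defensible choice. The difference matters only for onsets around Days 16 and 17, after the stated end of collection. A window ending at the Day 14 visit could itself drop events: the SAP schedule allows that visit 3 days early, and early withdrawals may have no such visit.

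**Conclusion.** The later-month branch of SAP 4.3.5 is wrong as written. For every Day 1 date, it puts an onset recorded in the following month 28 to 31 days after Day 1, or on a date that does not exist. A true onset by Day 14 is then excluded from the treatment-emergent tables in both arms. This follows from the SAP's wording and the calendar alone and needs no assumption about event rates.

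The practical effect is unknown and probably small, because it depends on how many start dates lack a day. An onset on Day 16 or 17 is truly outside the peramivir window, so leaving that event out would agree with the definition. The documents do not show that any event has been lost. The point deserves correction because the error is certain whenever the branch is used, it touches a primary safety endpoint, and some groups are small enough for one event to show.

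**What to change.** Add to SAP 4.3.5: when the recorded onset month and year are later than those of Day 1 and the day is missing, impute the first day of the recorded month, but not later than the event's end date if known.

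For all 910 affected Day 1 dates this gives a real calendar date 1 to 13 days after Day 1, inside the window in both arms. In the worked case it gives 1 February, Study Day 8. The first of the month may count an event that truly began on Day 16 or 17, which is in line with the conservative handling elsewhere in the SAP.

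Leave the other branches and the treatment-emergent window unchanged. The cost is one SAP sentence and a small programming change.

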# 4.3.6. By Study Visit Displays

When data are collected serially over time, individual data presentations may include by-visit displays. For these presentations, visits will be presented according to the nominal visit as obtained from the CRF or laboratory data. If assessments are collected with multiple dates or times within a given visit, the result closest to the scheduled visit date will be used for summary presentations. If two measurements have the same distance to the expected date, the earlier value will be used. If a subject has multiple non-missing values on the same date, then the last one is used, as determined by the time collected, if available.

#### 4.3.7. Derived and Transformed Data

TCID50 will be log10 transformed prior to performing the analyses.

#### 4.3.8. Definitions and Terminology

#### Age

Age will be defined as the age in days for the cohort of subjects <28 days old, months for the cohort of subjects from 28 days - 2 years, or years for the cohorts of subjects greater than 2 years old at the time of randomization. For all subjects, age in years will also be derived and rounded down to the tenth decimal place for the summary statistics that are presented for all subjects combined.

#### Confirmed Influenza

A subject will be confirmed as having acute influenza infection if any specimen for assay of influenza A or B antigen by RT-PCR obtained during the study is positive.

#### Baseline Value

For purposes of analysis, the baseline value is defined as the last value obtained prior to initiation of study drug (e.g., the Baseline Pre-Dose value). Should this value be obtained after the injection of study drug, then the most recent value obtained prior to initiation of study drug will be used for the baseline value.

#### Day 1

Day 1 is the day/time that study drug is initiated.

# Study Day

Study Day is defined relative to Baseline (Day 1). Thus, the study day of an event is calculated as: Study Day = event date – date of Day 1 +1.

# Days on Study

Days on Study is the number of days from Day 1 to the date of study completion or early termination as recorded on the EARLY TERMINATION/STUDY COMPLETION CRF.

# Days of Subject Diary Completion

Days of Subject Diary Completion is defined as the number of days from Day 1 to the date of last Subject Diary completion. For the purposes of this analysis, the date of last Subject Diary completion is defined as the last date in which the Subject Diary had at least one complete assessment of symptoms recorded.

# **Alleviation of Symptoms**

A subject has Alleviation of Symptoms if all of the assessed symptoms of influenza assessed on his/her subject diary based on age are either absent or are present at no more than mild severity level and at this status for a 21.5 hour (24 hours -10%) period.

# Composite Symptom Score

The Composite Symptom Score is defined as the sum of the symptoms of influenza (per age appropriate symptoms) assessed on a given time point within the subject diary.

# Initial Composite Symptom Score

The Initial Composite Symptom Score is defined as the Composite Symptom Score corresponding to the first assessment of a subject's symptoms.

# Resolution of Fever

A subject has Resolution of Fever if he/she has a temperature < 99.4°F oral or < 98.4°F axillary and no antipyretic medications have been taken for at least 12 hours. Resolution of Fever is based on information obtained from the individual subject diaries.

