10. STUDY CONDUCT

10.1. Overview

Up to 140 subjects will be enrolled in this study according to the following age groups:

- Birth to < 28 days: up to 10 subjects, given IV peramivir
- 28 days to < 2 years: up to 20 subjects: subjects enrolled after the approval of amendment 3 will receive IV peramivir
- 2 < 4 years: up to 10 subjects: subjects enrolled after the approval of amendment 3 will receive IV peramivir
- 4 < 7 years:up to 30 subjects: subjects enrolled after the approval of amendment 3 will receive IV peramivir
- 7 < 13 years:up to 40 subjects, randomized 4:1 to IV peramivir or oral oseltamivir
- 13 < 18 years:up to 30 subjects, randomized 4:1 to IV peramivir or oral oseltamivir

Once an age cohort is filled, enrollment in that cohort will be closed and communicated with all investigators.

A subject's duration of participation in this study is expected to be 14 days.

Subjects meeting the inclusion/exclusion criteria may be enrolled into the study. It is expected that most subjects will have the Screening/Baseline Visit and the Day 1 Treatment Visit on the same day.

All subjects will receive either a single dose of IV peramivir (600 mg, or12 mg/kg or 8 mg/kg or depending on age) or oral oseltamivir, dosed BID for 5 days. *Note, as of the approval of amendment 3, no additional subjects will be randomized to receive oseltamivir.*

Subjects will undergo follow-up assessments on Days 3, 7, and 14. The Day 3 visit may be a home visit (performed by a qualified study nurse). Day 7 is required to take place in the clinic, and Day 14 may either be a clinic visit, home visit, or follow-up phone call to the subject/parent/guardian.

All parents/caregivers will record the following information in the Subject Diary.

- Temperature measurements (oral or axillary) will be taken with an electronic thermometer provided by BioCryst, approximately every 12 hours until temperature normalizes for 48 hours (i.e., temperature without antipyretic is < 99.4 orally in children ≥ 6 and < 98.4 axillary in children < 6 years old for 4 measurements). With the exception of the baseline measurement, all temperature measurements will be obtained at least 4 hours after, or immediately before, administration of oral acetaminophen or other antipyretic medications, if taken.
- Date and time of oral oseltamivir dose administration, if applicable. This should be recorded in the Subject Diary twice a day for 5 days.

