13.8.2. Effectiveness Analyses

Time to resolution of fever, defined as a temperature < 99.4 oral or < 98.4 axillary with no antipyretic medications taken for at least 12 hours, will be estimated for each age group and overall by treatment group using the method of Kaplan-Meier. Subjects who do not achieve resolution of fever will be censored at the time of their last assessment.

Time to resolution of influenza symptoms, defined as the time from initiation of study drug until the start of the 21.5-hour period (24 hours- 10%) where all symptoms of influenza are recorded as none or mild, will be estimated for each age group and treatment group using the method of Kaplan-Meier. Subjects who do not experience alleviation of symptoms will be censored at the time of the last non-missing symptom assessment. As the number and type of symptoms varies by age, the analysis of time to resolution of symptoms will not be presented as an overall assessment.

Reduction in viral shedding will be assessed as the change from baseline in log₁₀ TCID₅₀/mL and RT-PCR, and will be summarized for each age group, treatment group and study visit.

Changes in virus susceptibility to neuraminidase inhibitors between virus cultured at Baseline and the last post-treatment sample from which virus can be cultured will be assessed using virology laboratory tests. Virology laboratory tests will include phenotypic characterizations of influenza virus recovered (hemagglutinin and neuraminidase) and viral susceptibility to peramivir, and genotypic analysis of primary virus isolates. These analyses will be presented separately by age group and viral subtype.

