#### Time to Event

Time to a given event is defined as the number of hours from initiation of earliest study treatment until the event occurs. The unit of measurement will vary based upon the endpoint and its respective schedule of assessment.

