# **6.2.2.** Effectiveness Analyses

A subject's oral temperature will be summarized by age group and overall by study visit and treatment group. A subject has Resolution of Fever if he/she has an oral temperature <99.4°F oral or <98.4°F axillary and no antipyretic medications have been taken for at least 12 hours. The time to resolution of fever will be estimated for each age group and overall by treatment group using the method of Kaplan-Meier using temperature and symptom relief medication information obtained from the subject diary data. Subjects who do not have resolution of fever will be censored at the time of their last non-missing post-baseline temperature assessment.

Alleviation of symptoms will be determined by assessment of symptoms as reported on each Subject Diary. The time to alleviation of symptoms will be estimated overall and for individual symptoms for each age group by treatment group using the method of Kaplan-Meier. Subjects who do not experience alleviation of symptoms will be censored at the date of their last non-missing post-baseline assessment.

Change from baseline in  $TCID_{50}/mL$  through Day 3, Day 7 and Day 14 respectively will be presented by age group and overall by treatment group for subjects with positive viral titers at baseline ( $log_{10} \ TCID_{50}/mL > 0.5$ ). A box plot and a histogram of the  $TCID_{50}/mL$  values will be presented by visit, age group, and treatment group. In addition, the median change from baseline in  $TCID_{50}/mL$  will be presented by visit, age group, and treatment group.

The number and percent of subjects with positive viral titers at baseline ( $log_{10} TCID_{50}/mL > 0.5$ ) that are shedding virus at each visit will be presented by age group and overall by treatment group.

The RT-PCR results at each visit will be presented by age group and overall by treatment group for subjects with positive RT-PCR results at baseline.

Change from baseline to last positive value of influenza virus susceptibility to neuraminidase inhibitors will be assessed using virology laboratory tests. Virology laboratory tests will include phenotypic characterizations of influenza virus recovered (hemaglutinin and neuraminidase) and viral susceptibility to zanamivir, oseltamivir, and peramivir, as well as genotyping of virus isolates. These analyses will be presented overall and by age group, treatment group and viral subtype.

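### Fever counts as resolved at the first eligible diary reading below threshold, with no requirement that it stay down, so transient dips bias the Kaplan-Meier time short

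*SAP*

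**What the plan says.** SAP 4.3.8 (Resolution of Fever) counts a child as resolved who "has a temperature < 99.4°F oral or < 98.4°F axillary and no antipyretic medications have been taken for at least 12 hours", using diary data. SAP 6.2.2 repeats the rule for the analysis: "oral temperature <99.4°F oral or <98.4°F axillary and no antipyretic medications have been taken for at least 12 hours". Protocol 13.8.2 agrees: "defined as a temperature < 99.4 oral or < 98.4 axillary with no antipyretic medications taken for at least 12 hours". SAP 4.3.8 (Time to Event) measures time as the "number of hours from initiation of earliest study treatment until the event occurs". None of these places asks for a confirming reading, a minimum afebrile period or absence of relapse.

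Two other parts of the plan use a duration. For symptom alleviation, SAP 4.3.8 requires that all assessed symptoms "are either absent or are present at no more than mild severity level and at this status for a 21.5 hour" period, and time runs to the start of that period. For diary recording, protocol 10.1 has temperatures taken "approximately every 12 hours until temperature normalizes for 48 hours". It spells this out as readings below threshold without antipyretic, for example "< 98.4 axillary in children < 6 years old for 4 measurements".

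One safeguard exists: protocol 9.8.4 and 10.3.1 exclude from the effectiveness analyses any temperature taken less than 4 hours after an antipyretic.

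**The concern.** A child with one low reading who is febrile again 12 hours later is an event and leaves the risk set. The 12-hour antipyretic condition and the 4-hour exclusion deal with drug-induced dips. They do not deal with natural variation over the day or with error in oral or axillary readings taken at home.

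Time to resolution of fever is a listed secondary endpoint (protocol 7.1.2), and SAP section 10 gives it its own Kaplan-Meier plot and a figure of medians with 95% CI. What is at stake is whether those medians describe lasting recovery or the first low reading. The symptom curves reported beside them use the stricter, sustained standard.

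**Working it through.** **Step 1: the definitions side by side**

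| Item | Where | State required | How long it must last |
|---|---|---|---|
| Fever endpoint | SAP 4.3.8, 6.2.2; protocol 13.8.2 | Below route-specific threshold; no antipyretic for 12 h | Not stated for temperature |
| Symptom endpoint | SAP 4.3.8; protocol 13.8.2 | All symptoms absent or mild | 21.5 h |
| Diary temperature recording | Protocol 10.1 | Below threshold without antipyretic | 48 h, 4 measurements |

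The third row tells caregivers when they may stop measuring. It does not define an endpoint.

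**Step 2: direction of the bias**

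A sustained afebrile period that starts under the same 12-hour antipyretic condition begins with a reading that also meets the single-reading rule. So for every child the single-reading time is no later than the sustained time, and it is earlier whenever an isolated dip came first. This follows from the definitions and needs no assumed rate.

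**Step 3: illustrative size**

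The plan states no figure to reproduce, and the inputs here are assumptions. Take a child who is still febrile for k = 4 readings at 12-hour intervals (about 48 h). All four are eligible and independent, and each has probability p of falling below threshold. Let q = 1 − p. All later readings are normal.

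- Any dip: 1 − q⁴.
- Resolved and then febrile again: (1 − q⁴) − (p⁴ + qp³ + q²p² + q³p). The bracket removed contains the courses in which no febrile reading follows the first dip.
- The same under a rule of two consecutive readings: p²(1 − p²) + q²p².
- The same under a rule of three consecutive readings: p³q. Three readings span 24 h, and three is the fewest at 12-hour intervals that cover 21.5 h.
- Mean hours called early, single reading: 12 × [4 − (q + q² + q³ + q⁴)].

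For p = 0.10: 1 − 0.6561 = 0.3439. The bracket is 0.0001 + 0.0009 + 0.0081 + 0.0729 = 0.0820. The difference is 0.2619.

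| p | Any dip | Single rule: resolved, then febrile | Two readings: same | Three readings: same | Mean hours early, single rule |
|---|---|---|---|---|---|
| 5% | 18.5% | 14.0% | 0.5% | 0.01% | 5.7 |
| 10% | 34.4% | 26.2% | 1.8% | 0.09% | 10.9 |
| 20% | 59.0% | 45.4% | 6.4% | 0.64% | 19.7 |

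The any-dip column includes dips that run straight into true recovery, so the next column is the one that matches the concern. The result also depends on k: any dip is 9.8, 19 or 36% for k = 2, and 26.5, 47 or 74% for k = 6.

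**Step 4: are the data there?**

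Four readings 12 h apart span 3 × 12 = 36 h, which is more than 21.5 h. A 21.5-hour window therefore fits inside the recording already planned, and a child with a single dip is still being measured.

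**The case against.** **The plan is internally consistent.** Protocol and SAP give the same endpoint rule. A reader might infer that the 48-hour diary text is a competing definition. It is not, because it only ends recording. This stands: the point is a choice of analysis, not a conflict between documents.

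**The single reading is inferred.** Protocol 13.8.2 could be read as a combined state, afebrile and free of antipyretic, lasting 12 hours. That reading is strained in SAP 4.3.8 and 6.2.2, where the 12 hours attach to antipyretics alone. Even if it were intended, 12 hours is still less than 21.5, and the wording would need repair.

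**The percentages are assumed.** This stands. The dip rate has no source in the documents, successive readings are unlikely to be independent, and a febrile child who is being given antipyretics has fewer eligible readings. The oral threshold also lies 100 − 99.4 = 0.6°F below the oral entry criterion, which leaves some margin against noise.

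**The arms.** A reader might infer that false early events pull the arms together and hide a difference. No between-arm calculation supports that. The study tests no hypothesis (protocol 13.3), and protocol 13.4 implies only about 140 − 117 = 23 children on oseltamivir.

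**Rebound is visible elsewhere.** Temperature is summarised by visit and listed, and antipyretic doses are summarised by study day. This is true, but none of these outputs corrects the Kaplan-Meier estimate.

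**Conclusion.** The point holds as a modest, inexpensive improvement. As written, the first eligible reading below threshold is the event, and the estimated time is biased short relative to sustained resolution. That direction follows from the definitions. The size does not: 14, 26 or 45% resolved and then febrile again is an illustration for assumed dip rates of 5, 10 or 20% over four independent, eligible readings, and antipyretic use would lower it. The documents support neither a claim of contradiction with the diary rule nor a claim about the between-arm difference. Type I error is not at issue. The consequence is limited to descriptive medians and curves for one secondary endpoint in a study whose primary objective is safety.

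**What to change.** Define time to resolution of fever as the start of the first period of at least 21.5 h in which all eligible diary readings stay below the route-specific threshold. If the sponsor prefers to keep the present definition, add this as a pre-specified sensitivity analysis. In either case:

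- Apply the existing 12-hour antipyretic-free condition at the start of the period, and leave out readings taken less than 4 h after an antipyretic, as the protocol already does. Applying the 12-hour condition to every reading would in effect demand 21.5 + 12 = 33.5 antipyretic-free hours. The trade-off is that a child given an antipyretic within the window can still count as resolved, so this choice should be stated openly.
- State how a missing or ineligible reading inside the window is handled. SAP 4.3.4 carries symptom scores forward but gives no such rule for temperature.
- Report the single-reading result alongside, so that the effect of the definition is visible.
- Record the change in SAP section 7, because protocol 13.8.2 carries the same definition.

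The cost is SAP wording and one extra table, with no new data collection. The downside is longer medians and more censored children, to an extent that the documents do not allow to be quantified.
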